7.1 Study Procedures/Evaluations

7.1.1 Study Specific Procedures

After written informed consent, participants will complete the baseline assessment (i.e., TP0) and be randomly assigned to the MBSR or HEP group in a permuted block design stratified by receipt of chemotherapy (i.e., two strata). To reduce bias, research staff who assess participants, as well as the PI, will be blinded to group assignment. At regional community centers, the MBSR group will receive training from a trained instructor during a group-based, approximately 2.5-hour manualized educational activity weekly for eight weeks. Participants will be asked to complete daily 45-minute mindfulness activities on days the group does not meet and a one-day weekend retreat (approximately 7 hours) to reinforce learning. HEP, which was developed to serve as an active control to MBSR, will receive manualized health education, without mindfulness instruction, using similar modalities for a matched schedule with the same time requirements. Participant engagement will be assessed through attendance records, and by percentage of homework completed and mindfulness activities during study participation assessed using REDCap diaries. Assessments will be done at three time points (see Figure – MBSR Study Schema): within three weeks pre-randomization (TP0), within three weeks after completion of the intervention (TP1), and three months (+/- 1.5 weeks) post intervention (TP2). Functional and structural brain imaging will be done at the NYU Center for Brain Imaging at TP0 and TP1. Neuropsychological tests and blood draws will be completed at the Bluestone Center for Clinical Research, Meyers College of Nursing, or New York University Center for Brain Imaging at TP0 and TP2. Neuropsychological tests will not be performed at the post-intervention assessment (i.e., TP1) due to likelihood of practice effects at that interval (i.e., two months). Patient-reported outcomes (see Patient-Reported Outcomes below for detail of these study measures) will be assessed at each time point.

Demographic and Clinical Characteristics. Demographic and clinical characteristics will be collected by patient self-report at TP0 and confirmed, when possible, by medical record review. A list of concomitant medications will be collected from participants at each study visit and confirmed, when possible, by medical record review.

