MRI. Functional MRI (fMRI) and diffusion MRI (dMRI) scans will be collected at TP0 and TP1 using a 3T Siemens Prisma scanner (Erlangen, Germany). Total time to obtain the neuroimaging scans is approximately one hour at each of these time points. During fMRI, participants will complete the emotional faces n-back (EFNBACK) task,⁶² which engages working memory while evaluating the impact of emotional distractors. Participants will complete a resting state fMRI scan (i.e., fcMRI) before the EFNBACK to evaluate the activity of the brain in its default mode.^{10,63} dMRI will evaluate white matter integrity.

Neuropsychological Function. Neuropsychological function will be evaluated with a battery of well-validated measures in the NIH Toolbox at TP0 and TP2.⁵⁷ Total time to administer these tests is approximately two hours at each of these time points.

Patient-Reported Outcomes. Patient-reported outcomes will be collected at each time point (i.e., TP0, TP1, TP2). Subjective cognitive function will be assessed with the Patient Assessment of Own Functioning Inventory,⁵⁸ Attentional Function Index,³³ and PROMIS-Cognitive.⁵⁹ Affect will be assessed with the PROMIS measures⁶⁰ and subjective measures of worry (i.e., Three-Item Worry Index,⁶¹ Cancer-Specific Worry Index¹⁰). Fatigue and sleep disturbance will be assessed with the PROMIS measures.⁶⁰ Self-reported stress will be assessed with the Perceived Stress Scale.⁵⁵ Dispositional mindfulness will be measured with the Mindful Attention Awareness Scale (MAAS).⁷⁸ Total time to administer the self-report

CONFIDENTIAL

measures is approximately 30 minutes.

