- Record participant's adherence to intervention program using REDCap diary, which can be completed during the study visit or at home.

7.3.3.7 Visit 9

CONFIDENTIAL

Week 7 of intervention

- Administer the study intervention in accordance with the MBSR or HEP manual, as appropriate to randomization. Both interventions will include the weekly in-person group meeting and homework completed on all other days, with the same time requirements.
- Record participant's adherence to intervention program using REDCap diary, which can be completed during the study visit or at home.

7.3.3.8 Visit 10

Week 7 of intervention

- One-day weekend retreat in accordance with MBSR or HEP manual (may be completed in week 6 or week 7)

7.3.3.9 Visit 11

Week 8 of intervention

- Administer the study intervention in accordance with the MBSR or HEP manual, as appropriate to randomization. Both interventions will include the weekly in-person group meeting and homework completed on all other days, with the same time requirements.
- Record participant's adherence to intervention program using REDCap diary, which can be completed during the study visit or at home.

7.3.4 Visit 12

TP1 (short-term follow-up assessment within three weeks of completion of intervention)

- Confirm that eligibility criteria have not changed since TP0 assessment.
- Collect 15 ml (1 tablespoon) of blood for biobanking.
- Obtain any changes in demographic information, medical history, medication history, and alcohol and tobacco use history.
- Assess for any adverse events, serious adverse events, or unexpected problems.
- Complete patient-reported outcome measures.
- Study personnel or MRI technologist to confirm MRI safety screen.
- Conduct urine and saliva toxicology screen.
- Practice fMRI task.
- Complete MRI scan.
- Complete study assessment questionnaire.

Note: Between visit 10 and the final study visit, all participants will continue to complete weekly REDCap diaries of mindfulness activities to evaluate whether findings at three months post intervention (i.e., TP2) vary by level of continued mindfulness activities in the MBSR group or contamination of new mindfulness activities in the HEP group.

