**Aim 1: Evaluate the preliminary efficacy of MBSR to improve neural markers of cognitive changes during AI therapy.** **fMRI:** Data will be preprocessed using Statistical Parametric Mapping-12 (SPM-12; [www.fil.ion.ucl.ac.uk/spm](http://www.fil.ion.ucl.ac.uk/spm)) to normalize images into standard space so that all brains can be compared. Talairach PickAtlas will be used to define regions of interest (ROIs) for cognitive and emotion processing. Neural activation will be evaluated using the blood-oxygen-level-dependent (BOLD) signal. SPM-12 will extract BOLD activation in these ROIs. Brain activation maps will describe (1) between-group differences in brain activation in ROIs for the MBSR versus active control group pre- and post-intervention and (2) within-group change scores in brain activation for each group pre- to post-intervention. **fcMRI:** BOLD signal time series will be extracted from ROIs of the default mode network. Physiological noise and motion artifact regressors will be removed. Residual time series from each ROI will be filtered between 0.01-0.08 Hz. Analyses will be performed with and without a global signal regressor to assess impact on connectivity. Parameter estimates representing connectivity between neural regions will be extracted. Functional connectivity maps will describe between-group differences in connectivity in ROIs pre- and post-intervention and within-group change scores in connectivity pre- to post-intervention. **dMRI:** Data will be analyzed using ExploreDTI ([www.exploredti.com](http://www.exploredti.com)), FreeSurfer ([surfer.nmr.mgh.harvard.edu](http://surfer.nmr.mgh.harvard.edu)), and the diffusion toolbox of the Functional MRI tool of Brain Software Library ([www.fmrib.ox.ac.uk/fsl](http://www.fmrib.ox.ac.uk/fsl)) to perform quality assurance for images, process them for characterization of the integrity of white matter tracts, and match white matter tracts to structural MRI data. White matter tracts between cortical and subcortical ROIs will be evaluated to describe how white matter integrity is affected. Fractional anisotropy (FA) values for white matter tracts will be extracted. FA maps will describe (1) between-group differences in FA in ROIs for the MBSR versus active control group pre- and post-intervention and (2) within-group change scores in FA pre- to post-intervention.

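### SAP Aim 1 never names the between-arm difference in change; the task-fMRI change it does name is within-arm and may include practice on a repeated working-memory task

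*SAP*

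**What the plan says.** Protocol 4.2.1 sets the primary endpoint as effect sizes for change in neural markers, before to after, for MBSR against HEP. Protocol 10.4.2 leaves the analysis to the SAP.

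SAP Aim 1 is headed as the evaluation of preliminary efficacy. For task fMRI it lists two outputs. The first is "between-group differences in brain activation in ROIs for the MBSR versus active control group pre- and post-intervention". The second is "within-group change scores in brain activation for each group pre- to post-intervention". The resting-state and diffusion paragraphs follow the same pattern. No between-arm difference in change is named, neither output is given priority, and practice on the task is not mentioned.

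On timing, Protocol 7.1.1 says: "Neuropsychological tests will not be performed at the post-intervention assessment (i.e., TP1) due to likelihood of practice effects at that interval (i.e., two months"). The same section says "Functional MRI (fMRI) and diffusion MRI (dMRI) scans will be collected at TP0 and TP1" and that during fMRI "participants will complete the emotional faces n-back (EFNBACK) task", "which engages working memory while evaluating the impact of emotional distractors". The entry "Practice fMRI task" appears before the TP0 scan (7.3.2, Visit 2) and again before the TP1 scan (7.3.4, Visit 12). Table A agrees.

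SAP Aims 2a and 2b correlate the Aim 1 change scores with changes in cognition and affect. Aim 2a switches to baseline markers if no neural change is found, without saying which contrast or threshold decides that.

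**The concern.** The protocol withholds cognitive tests at TP1 because practice would cloud them, then repeats a working-memory task in the scanner at that visit. If familiarity alters activation, an arm's TP0-to-TP1 task-BOLD change is intervention plus practice. The only change the SAP names is of this kind.

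Two things are at stake. First, the trial exists to supply effect sizes for a later R01 (Protocol 4.2.1 and 10.2). A within-arm effect size taken forward from Aim 1 would carry any practice shift with it, whether or not a p-value is attached. Second, the Aim 2a switch depends on whether change is found. If that is read off within-arm change, practice could decide which analysis is run.

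The missing contrast is a gap for all three imaging types. The practice argument applies to task fMRI only. It does not apply to fractional anisotropy, and it applies less directly to resting-state connectivity.

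**Working it through.** **Inputs.** From Protocol 10.5: 16 per arm, effect size 1, two-sided alpha 0.05, two-sample equal-variance t-test, stated power 78.1%. Assumed, because neither document gives it: a practice shift of 0.2 to 0.8 SD of the change score, equal in both arms, with no effect of either programme.

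**1. The plan's own figure.** Noncentral t, df = 2×16 − 2 = 30, noncentrality = 1×√(16/2) = 2.83. Power = 0.781, which matches. That calculation is for a between-arm test.

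**2. What each contrast estimates.** Let m and h be the programme effects and p_M and p_H the mean practice shifts.

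- Within MBSR: change = m + p_M
- Within HEP: change = h + p_H
- Difference in change = (m − h) + (p_M − p_H), which is m − h when practice is equal
- Difference between arms at TP1 = the line above plus any chance baseline difference

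Equal practice therefore cancels from both between-arm contrasts and stays in both within-arm ones. Of these, the difference in change is the one that matches 4.2.1.

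**3. Illustration of size.** For a within-arm paired test, df = 15 and noncentrality = shift × √16. The misleading pattern of MBSR changing and HEP not changing has probability p(1 − p), where p is the within-arm rejection rate. The last column comes from 40,000 simulated trials.

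| Assumed shift (SD of change) | Noncentrality | Within-arm test rejects | MBSR rejects, HEP does not | Difference in change rejects |
|---|---|---|---|---|
| 0.2 | 0.8 | 11.6% | 0.116×0.884 = 10.3% | 5.0% |
| 0.3 | 1.2 | 20.3% | 0.203×0.797 = 16.2% | 5.2% |
| 0.5 | 2.0 | 46.5% | 0.465×0.535 = 24.9% | 5.0% |
| 0.8 | 3.2 | 84.8% | 0.848×0.152 = 12.9% | 4.9% |

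Without any test, the average within-arm standardised effect in the simulation was 0.21, 0.32, 0.53 and 0.84. It returns the practice shift, slightly inflated. The mean between-arm difference was about 0 throughout.

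**4. Aim 2 correlations.** Adding a constant c to every woman's change leaves the correlation as it was: corr(X + c, Y) = corr(X, Y). A shift common to all women does not disturb these results.

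**5. Power of the between-arm estimate.** If the effect size of 1 refers to change scores, power stays at 78.1%. If it refers to raw scores, it depends on the pre-post correlation r, which is not documented:

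| Assumed r | Change score: 1/√(2(1 − r)) | Power | Baseline-adjusted: 1/√(1 − r²) | Power |
|---|---|---|---|---|
| 0.3 | 0.85 | 64% | 1.05 | 82% |
| 0.5 | 1.00 | 78% | 1.15 | 88% |
| 0.7 | 1.29 | 94% | 1.40 | 97% |

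The 95% interval on the between-arm difference in change has half-width 2.042×√(2/16) = 0.72 SD of change.

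**The case against.** The strongest reply is that efficacy is already comparative. Protocol 4.2.1 defines it as MBSR versus HEP, 10.5 powers a two-sample test, and the SAP has within-group change described for each group, so HEP's change will sit beside MBSR's. The difference in change can also be recovered from either listed output, since (M1 − H1) − (M0 − H0) = (M1 − M0) − (H1 − H0). This largely stands. A reader might infer that MBSR's within-arm change will be reported as efficacy, but the documents do not say so. What remains is that the SAP, to which the protocol defers, leaves the choice of estimate open. Two separate sets of maps also do not give the standardised effect size or interval for the difference.

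Second, no within-arm test or threshold is planned, and the SAP says the sample is too small for inference. This stands. The rejection rates above are arithmetic on assumed shifts, not this trial's error rates.

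Third, the practice statement in 7.1.1 concerns the neuropsychological battery, and BOLD is not a performance score. Neither document says that activation in this task shifts with repetition, in which direction, or by how much. The rehearsal before each scan may also reduce any shift, although neither document presents it as a control for practice. This stands as a limit. The extension is reasonable (a cognitive task, the same women, the same visit), but it is an inference.

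Two further readings are tempting and unsupported. One is that practice distorts the Aim 2 correlations. A common shift does not, and nothing documents practice that varies between women. The other is that women must be trained to an accuracy criterion before the TP0 scan. That is one design option, no documented failure calls for it, and the manual of procedures, which may address rehearsal, is held separately.

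**Conclusion.** The point holds as a clarification of moderate weight in the SAP, not as a flaw in the randomised design. Followed literally, Aim 1 names only one kind of change, the within-arm kind. For task fMRI that is the quantity shared practice can move, and it is not the one the primary endpoint describes. The undefined Aim 2a switch could inherit the same ambiguity.

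The size is unknown because the documents give no practice effect for the task. Under assumed shifts of 0.2 to 0.8 SD, the within-arm effect size is overstated by about that amount, while the between-arm difference in change is unaffected. This rests on practice being similar in the two arms, which is plausible because both complete the same scans and rehearsals on the same schedule.

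**What to change.** In SAP Aim 1:

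- Name the between-arm difference in TP0-to-TP1 change, or the baseline-adjusted TP1 difference, as the efficacy estimate for each imaging type. Report it with an interval, and make it the effect size carried into R01 planning.
- State that within-arm task-BOLD change is descriptive, may include practice, and is reported for both arms together.

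In SAP Aim 2a, state that within-arm change does not decide whether neural change has been found. Either tie that decision to the between-arm estimate by a stated rule, or describe the change and baseline correlations in every case.

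The cost is a few sentences. No extra women, visits or scans are needed, because the data are already collected. The price is that MBSR's within-arm change can no longer be quoted on its own as an effect, and the estimate that replaces it is imprecise at 16 per arm (about ±0.72 SD of change). Baseline adjustment recovers some precision.

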SOP	Standard Operating Procedure
SPSS	Statistical Package for the Social Sciences
US	United States

Protocol Summary

[figure not shown]
Title	Mindfulness-Based Stress Reduction To Improve Cognitive Function During Aromatase Inhibitor Therapy
Short Title	NA
Brief Summary	This study will use non-invasive neuroimaging (i.e., MRI) to examine whether Mindfulness-Based Stress Reduction (MBSR) improves neural markers of changes in cognitive function for postmenopausal women taking aromatase inhibitor (AI) therapy for breast cancer. The pilot randomized controlled trial will obtain preliminary efficacy of MBSR versus Health Enhancement Program (HEP) active control to improve neural markers of changes in cognitive function. The final sample will include 32 postmenopausal women with breast cancer. MBSR and HEP groups will meet for a matched schedule of 8 weekly 2.5-hour sessions and a one-day weekend retreat. Specimen and data collection will be done at three time points: pre-randomization (i.e., within three weeks before beginning the intervention), within three weeks after completion of the intervention, and approximately three months (+/- 1.5 weeks) post intervention. To obtain effect sizes, change scores for neuroimaging parameter estimates will be correlated with change scores for measures of neuropsychological function and affect. Differential expression of genes will be associated with change scores in neuroimaging parameter estimates.
Phase	Preliminary efficacy
Objectives	The primary aim is to (1) evaluate the preliminary efficacy of MBSR to improve neural markers of changes in cognitive function during AI therapy. The exploratory, hypothesis generating aims are to (2) describe relationships between neural markers and (a) neuropsychological function and (b) affect during MBSR; and (3) explore the moderating effect of inter-individual differences in the expression of genes involved in stress responses on neural markers of changes in cognitive function during MBSR.
Methodology	Single blind, randomized controlled trial
Endpoint	Primary endpoint: Changes in neural markers of cognitive function Exploratory endpoints: Changes in neuropsychological function and affect; moderating effect of differential expression of genes involved in stress responses
Study Duration	Three years
Participant Duration	Approximately seven months
Duration of behavioral intervention	Eight weeks

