3.2 Secondary Objectives

The **exploratory, hypothesis generating aims** are to (2) describe relationships between neural markers and (a) cognitive function and (b) affect during MBSR; and (3) explore the moderating effect of inter-individual differences in the expression of genes involved in stress responses on neural markers of changes in cognitive function during MBSR.

4 Study Design and Endpoints

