4.2.3 Exploratory Endpoints

Exploratory endpoints will include correlations between neural markers of changes in cognitive function (or baseline neural markers if no changes are found) and changes in (a) cognitive function from before to

CONFIDENTIAL

three months after MBSR versus HEP and (b) self-reported affect from before to within three weeks after and three months (+/- three weeks) after the intervention. Exploratory endpoints will also include the moderating effect of inter-individual differences in the expression of genes involved in stress responses on neural markers of changes in cognitive function. Exploratory endpoints were chosen to gain preliminary evidence of relationships between neural markers and objectively and subjectively measured cognitive and affective phenotypes, as well as to gain preliminary evidence for underlying biological mechanisms (i.e., gene expression). See Figure 1 for a graphical representation of these relationships.

5 Study Enrollment and Withdrawal

The R00 study will enroll up to 32 evaluable participants (i.e., 16 per group) for the pilot randomized controlled trial. Up to 40 participants will be enrolled to obtain this final sample size.

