**Statistical Analysis Plan (SAP) for R00NR015473**  
**August 8, 2017**

**Data analysis.** Data analysis will be performed using SPSS Statistics 24 (IBM Corp., Armonk, NY). Using exploratory and descriptive analyses, we will first evaluate whether any data anomalies (e.g., nonrandom missing data, erroneous outliers, multicollinearity, possible confounding) may invalidate planned analyses and then summarize data in terms of location and variability using appropriate descriptive statistics, given the variable's level of measurement and observed data distribution. As needed, appropriate remedial approaches (e.g., data transformations, imputation, nonparametric analysis methods) will be applied.

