**Exploratory Aim 2a: Describe relationships between neural markers and changes in cognitive function.** Change scores for neuroimaging parameters obtained in Aim 1 will be correlated with change scores on measures of cognitive function to describe how neural markers are associated with cognitive changes. If no changes in neural markers are found, relationships between baseline neural markers and changes in cognitive function will be described. **Exploratory Aim 2b: Describe relationships between neural markers and changes in affect.** The methods in 2a will be used to describe relationships between neural markers and changes in affect. **Exploratory Aim 3: Explore the moderating effect of inter-individual differences in the expression of genes involved in stress responses on the relationship between AI therapy and neural markers during MBSR.** Differential expression (DE) of genes in relation to fMRI, fcMRI, and dMRI parameter estimates at each time point will be determined using correlational analysis. Expression intensity varies widely over genes and needs to be adjusted between genes to provide a reliable measure of DE. We will adjust the standard errors and estimate the correlation of genes with each outcome. We will adjust for multiple hypothesis testing through estimation of the FDR using the Benjamini-Hochberg procedure. The FDR q-value will be determined empirically.

**Possible Problems and Solutions.** The sample size is too small to make inferences about relationships evaluated in the R00 study to the larger population of postmenopausal women with breast cancer. The effect sizes for these relationships will be determined in the R00 study, which will inform the sample size for a well-powered study planned for future R01 applications (see Plan for Research Independence in the Final Progress Report for the K99 Phase). If no relationships are found between gene expression levels for stress response pathways and neural markers, other pathways will be evaluated (e.g., DNA repair).

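### SAP Aims 2a and 2b do not say how treatment arm enters the change-score correlations; pooled without adjustment, they would mix the between-arm difference with the within-arm association

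*SAP*

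**What the plan says.** The SAP's method for Exploratory Aim 2a is one sentence: "Change scores for neuroimaging parameters obtained in Aim 1 will be correlated with change scores on measures of cognitive function". For Aim 2b it adds: "The methods in 2a will be used to describe relationships between neural markers and changes in affect". The Protocol Summary gives the same method and its purpose: "To obtain effect sizes, change scores for neuroimaging parameter estimates will be correlated with change scores for measures of neuropsychological function and affect". None of these names a coefficient, an analysis set for Aim 2, or a role for treatment arm or chemotherapy stratum. Protocol 10.4.13 only refers back to the SAP.

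Other places bear on how arm might enter:

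- Protocol 10.3 defines a single analysis dataset containing everyone randomised.
- Protocol 4.2.3 words the exploratory endpoint with both arms in view: "three months after MBSR versus HEP and (b) self-reported affect".
- Protocol 3.2 words the aim as "describe relationships between neural markers and (a) cognitive function and (b) affect during MBSR", which could mean the MBSR arm alone.
- SAP Aim 1, the source of the neural change scores, describes "within-group change scores in brain activation for each group pre- to post-intervention".
- The SAP's opening data check covers "nonrandom missing data, erroneous outliers, multicollinearity, possible confounding", without naming arm or Aim 2.

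Protocol 10.2 and the SAP's closing paragraph both say the sample is too small for inference to the wider population, and that the effect sizes obtained will inform the sample size of a later R01 study.

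**The concern.** The sample consists of two randomised arms. The hypothesis in Protocol 2.2 is that stress reduction acts on neural markers and thereby improves cognition and affect. If it does, the arms differ in mean on both variables in each correlation. A correlation over all participants that ignores arm then picks up that mean difference as well as the association between patients in the same arm.

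The two quantities answer different questions. That MBSR moves a neural marker and also moves a cognitive score does not show that patients with more neural change have more cognitive change. A pooled r could be read as showing this, and would then enter R01 planning as its effect size.

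**Working it through.** **The plan's own figure.** Protocol 10.5 gives 78.1% power for 16 per group, effect size 1, two-sided alpha 0.05 and an equal-variance t-test. With noncentrality 1 × √(16/2) = 2.828 and 30 degrees of freedom, the noncentral t gives 78.14%, so the figure reproduces. It concerns the arm comparison. The documents give no figure for the Aim 2 correlations.

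**Inputs.**
- Allocation: 16 per arm, 32 analysable (Protocol 10.5 and the study schematic).
- Neural arm effect d1 = 1: the conditional planning value in Protocol 10.5, used for illustration.
- Arm effect d2 on cognition or affect: not in the documents, so varied from −1 to 1.
- Within-arm correlation r_w: not in the documents, so taken as 0 and 0.30.

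**Formula.** With equal arms and within-arm SD 1, an arm difference d adds d²/4 to a variable's pooled variance, and the two differences add d1·d2/4 to the covariance. Hence

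pooled r = (r_w + d1·d2/4) / √[(1 + d1²/4)(1 + d2²/4)].

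For d1 = 1, d2 = 0.5, r_w = 0: 0.125 / √(1.25 × 1.0625) = 0.125 / 1.152 = 0.11. For d1 = d2 = 1, r_w = 0: 0.25 / 1.25 = 0.20.

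**Results for d1 = 1.**

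| d2 (assumed) | pooled r, r_w = 0 | pooled r, r_w = 0.30 |
|---|---|---|
| −1 | −0.20 | 0.04 |
| −0.5 | −0.11 | 0.15 |
| 0 | 0.00 | 0.27 |
| 0.2 | 0.04 | 0.31 |
| 0.5 | 0.11 | 0.37 |
| 1 | 0.20 | 0.44 |

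If both effects are only 0.5 and r_w = 0, pooled r is 0.0625 / 1.0625 = 0.06. The sign can also reverse: with r_w = −0.20 and d1 = d2 = 1, pooled r is (−0.20 + 0.25) / 1.25 = +0.04.

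**Check by simulation** (40,000 trials, 16 per arm, r_w = 0). The mean pooled r was 0.11 for effects of 1 and 0.5, and 0.20 for effects of 1 and 1. With arm means removed it was 0.00 in both cases.

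**Scale against sampling error.** The 95% interval around r = 0 is ±tanh(1.96/√29) = ±0.35 at n = 32, and ±tanh(1.96/√13) = ±0.50 within one arm of 16.

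**Consequence for planning (illustrative).** Suppose r_w = 0.30 and both arm effects are 1, so pooled r = 0.44. By Fisher's z, 80% power at two-sided 5% needs [(1.960 + 0.842)/atanh(r)]² + 3 participants: 39 for r = 0.44 and 85 for r = 0.30. With 39, power for the within-arm association is about Φ(atanh(0.30) × √36 − 1.96) = Φ(−0.10) = 46%.

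**The case against.** The strongest reply is that no passage says the arms are pooled. Aim 1 describes its change scores within each group, and Protocol 3.2 can be read as meaning the MBSR arm alone. Under a per-arm analysis the artefact is zero. This stands as far as it goes: a reader might infer that unadjusted pooling is the stated plan, and the documents do not support that. But they do not choose a per-arm analysis either, and the single all-randomised dataset points the other way.

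Other stronger readings also fail:

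- **That the trial expects a neural effect of d = 1.** Protocol 10.5 calls the intervention effect unknown and uses 1 only as a conditional value.
- **That d2 should be as large as d1.** Nothing supports this. Neural change runs from TP0 to TP1, while neuropsychological change runs from TP0 to TP2 (Protocol 7.1.1).
- **That false-positive rates are inflated.** Testing the pooled r at 0.05 would reject in 9% (effects 1 and 0.5) or 20% (1 and 1) of simulated trials, but no test is planned for Aim 2. The purpose is descriptive effect sizes.
- **That omitting the chemotherapy stratum biases the result.** No such bias has been shown.

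It can also be argued that covariation driven by the intervention is part of the hypothesised pathway, so adjusting for arm discards something of interest. That is a fair reason to keep the pooled correlation in view. It is not a reason to let it stand for the within-arm association.

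Finally, the SAP's check for possible confounding could catch the problem, but it is generic and leaves the choice until the data have been seen.

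**Conclusion.** The concern holds as an unspecified analysis whose most natural reading is open to bias. It does not show that a wrong analysis has been adopted. Under the illustrative neural effect of 1 and zero within-arm correlation, the bias reaches 0.20 only if the effect on cognition or affect is also 1. It is 0.11 at 0.5, 0.04 at 0.2, absent if either effect is zero, and negative if the effects have opposite signs. Where a within-arm correlation exists, pooling alters it in either direction.

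Every d2 and r_w here is an assumption. The bias is smaller than the sampling error of this pilot, but a confidence interval around the pooled r would not reveal it, and it would carry into the R01 calculation. The exploratory status of Aim 2 lowers the stakes without removing them.

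**What to change.** State in the SAP that Aims 2a and 2b use all randomised participants with analysable data. Report, with a 95% confidence interval, the partial correlation of the two change scores adjusted for arm, and name it as the estimate carried into R01 planning. Adjustment for chemotherapy stratum, the randomisation factor in Protocol 10.6.1, is optional. Show the pooled and per-arm correlations beside it as description. Per-arm estimates alone would be imprecise (about ±0.50), so the adjusted estimate from all 32 is useful even if a per-arm analysis was intended.

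The cost is one or two SAP sentences, a little more analysis and no new data. Precision hardly changes: the interval around r = 0 is ±tanh(1.96/√28) = ±0.35 with arm, and ±tanh(1.96/√27) = ±0.36 with arm and stratum.
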